12.0 Withdrawal of Subjects

At any time during the study, participants may ask to withdraw from the study. If the investigator feels that it is no longer safe for the participant to participate in the study, (i.e., the participant no longer meets the study eligibility criteria), the participant will be withdrawn from the study without their consent.

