- Given the scope of the K07 career development award, it is not feasible to seek tribal approval for contacting American Indian/Native American cancer patients who are included in the NMTR. Therefore, per standard NMTR policies and procedures when tribal IRB approval has not been obtained, American Indian and Native American cancer survivors will not be contacted by the NMTR on behalf of the study.

PROTOCOL TITLE: Whole-of-Day Approach to Physical Activity in Older Cancer Survivors

The second screening will take place by telephone approximately 5-8 days after the cancer survivor has received the letter from the study that further explains the intervention and invites participation. The study coordinator/recruiter will provide additional information about the study, answer questions, and assess eligibility.

3.2 Men and women 65 years (at time of study enrollment) and older who meet the following criteria are eligible:

- Diagnosed in NM within the past 5 years with a loco-regionally staged cancer, completed primary treatment (surgery, radiation, chemotherapy), and not currently being treated for a recurrence. Individuals on hormone therapy only are eligible. (See Table 1 for cancer types)
- Mild-to-moderate physical functional impairment (raw score between 15 and 29 on the 8-item PROMIS Physical Function survey); representing individuals most at risk for functional decline and most likely to benefit from a home-based lifestyle activity intervention based on our previous research. (A score of 15 represents 0.5 standard deviation [SD] below the population mean; a score of 29 represents 1.5 SD below the population mean)
- Able to speak, read, & understand English or Spanish.
- Participating in less than 120 minutes per week of MVPA (otherwise a program to increase MVPA would be more suitable)(determined using Godin Leisure Time Exercise Questionnaire – low respondent burden).
- Living independently and capable of walking 3 blocks (approximately 1300 steps or 0.25 mile) without an assistive device (e.g., cane, walker) and without stopping to rest.
- No severe impairments (in seeing or hearing) or pre-existing medical limitations for engaging in daily LPA (e.g., severe orthopedic conditions, pending hip/knee replacement, dementia, oxygen dependent, chronic vertigo).
- No paid employment or volunteer position for greater than 20 hours per week (to avoid potential confounding by occupation activity/inactivity)

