3.3 Exclusion Criteria

- Adults not able to consent are excluded from participation
- Based on the age criteria (65 years and older), individuals who are not yet adults (infants, children, teenagers) may not participate in this study due to the same age criteria above
- Pregnant women may not participate in this study due to the same age criteria above
- Prisoners may not participate in this study as this is a study of free-living individuals

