		X		X			Reminder to ppt about assessment (need another person present for physical function tests) (see Assessment Call 3 Script ...)
		X					Reminder to ppt about assessment (text from [name] with link to Zoom or Skype videoconference session for physical function tests)
		X					Remote assessment conducted / completed via Skype or Zoom
		X		X			Follow-up for incomplete surveys; return of activPAL (see Assessment Call 4 Script ...)
\$						X	Randomization and mail gift card: 
 • Group A: mail thank you (on card stock) and gift card; start intervention; mail cover letter, Fitbit, Fitbit instructions, & MI Visual Aids (1st 2 Health Coaching calls)

PROTOCOL TITLE: Whole-of-Day Approach to Physical Activity in Older Cancer Survivors

Fees/ Postage	Phone		Email		Mail		
 Group B: mail thank you letter (maintain usual activity for 12 weeks; then receive full intervention) and gift card.
	IN	OUT	IN	OUT	IN	OUT	
							Fitbit setup; verify receipt, ask if ppt would like help; reminder: maintain usual activity for 1 week; schedule 1 st health coaching call
		X					1 st Health Coaching Call; review Fitabase before call; record notes on MI Visual Aids;
		X					2 nd Health Coaching Call; review Fitabase before call; record notes on MI Visual Aids;
\$					X		Mail MI Visual Aids (calls 3-5)
		X					3 rd Health Coaching Call; review Fitabase before call; record notes on MI Visual Aids;
		X					4 th Health Coaching Call; review Fitabase before call; record notes on MI Visual Aids;
		X					5 th Health Coaching Call; review Fitabase before call; record notes on MI Visual Aids; Schedule 13-week Assessment 
 Schedule remote assessment w/ [name] via MYHealth calendar Ask survey preference (mail/online) (see Assessment Call 1 Script ...)
		X					Waitlist Control Group – 13-week Assessment: 
 Schedule remote assessment w/ [name] via MYHealth calendar Ask survey preference (mail/online) Inform ppt Fitbit will be mailed (see Assessment Call 1 Script ...)
				(X)		X	Survey packet & cover letter mailed to ppt (optional: email w/ REDCap link)
							Verify receipt of packet (see Assessment Call 2 Script ...)
		X		X			Reminder to ppt about assessment (need another person present for physical function tests) (see Assessment Call 3 Script ...)

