Quality of Life (secondary outcome): QOL will be measured using PROMIS (Patient-Reported Outcomes Measurement Information System) measures ⁶² . The 8-item short forms are used to assess domains in mental health (anxiety and depression), physical health (physical function, fatigue, pain, sleep disturbance, and sleep impairment) and social health (satisfaction with social roles and activities, i.e., social functioning). These instruments are valid and reliable for use in diverse clinical samples ⁶³⁻⁶⁶ . Surveys will be scored using the free HealthMeasures Scoring Service (https://www.assessmentcenter.net/ac_scoringservice). The service provides T-scores, which represent a linear transformation of the raw scores, normed to the general population, with a mean of 50 and a standard deviation of 10.	X	X	X

PROTOCOL TITLE: Whole-of-Day Approach to Physical Activity in Older Cancer Survivors

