13.0 Potential Risks to Subjects / Protection Against Risks

This trial poses minimal risk, since the intervention specifies only light-intensity physical activity (e.g., standing, walking), which the participants are likely to already be doing, and thus may just be increasing in frequency or duration. Individuals for whom unsupervised light-intensity activity is not appropriate will be excluded from the study per the eligibility criteria. Nevertheless, there are some potential risks associated with the objective measure of sedentary activity. Sedentary activity will be assessed with a small, light-weight monitor (ActivPAL3™) worn on the thigh, and attached to the skin via an adhesive. If the attachment

PROTOCOL TITLE: Whole-of-Day Approach to Physical Activity in Older Cancer Survivors

causes any discomfort or irritation during the one week of data collection, the monitor will be moved to a different location if possible.

The remote assessment of physical performance poses minimal risk, since the two performance tests primarily incorporate movements typically undertaken during normal daily activities (standing from a chair, sitting on a chair), and thus represent tests that are more likely to be safely performed in a home setting. Note that both the 30 second Chair Stand test and the 4-stage balance test (see **Table 2**) have been routinely conducted in adult populations with mild to severe functional impairment such as cerebral palsy, COPD, knee osteo-arthritis, low back pain, multiple sclerosis, Parkinson's disease, renal transplant, rheumatoid arthritis, stroke, vestibular disorders, and frail elderly.^{83,84} Also, remote assessment (using videoconferencing) of these physical performance tests were determined to be safe, with no adverse events.⁸⁵⁻⁸⁷

A friend or family member is required to be present during the physical performance testing that is self-administered by the study participant in their own home. This friend or family member must be physically and mentally capable of providing support if needed, and have access to a telephone to request medical help, if needed. Additional protection against risks during the physical performance tests will include the following:

- A fall assessment will be administered prior to the tests. Frequent fallers will require 2 people to stand nearby the study participant during the tests to provide support if needed.

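### Section 12 withdraws a participant judged unsafe from the whole study, and no visible text keeps the PROMIS physical function form going, so scores may be lost in people who have plausibly declined

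*Combined protocol and SAP*

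**What the plan says.** Section 12.0 covers voluntary withdrawal and withdrawal by the investigator. The investigator's rule begins "If the investigator feels that it is no longer safe for the participant to participate in the study" and explains this as the case where "the participant no longer meets the study eligibility criteria), the participant will be withdrawn from the study without their consent". Withdrawal from the study is the only action the section names.

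Several criteria in section 3.2 concern function or illness, for example being "capable of walking 3 blocks (approximately 1300 steps or 0.25 mile) without an assistive device" and "not currently being treated for a recurrence". Section 13.0 adds: "Individuals for whom unsupervised light-intensity activity is not appropriate will be excluded from the study per the eligibility criteria".

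Self-reported physical function is a primary endpoint (section 8.0; Table 2 in section 9.0). On the PROMIS measures, Table 2 states: "The 8-item short forms are used to assess domains in mental health (anxiety and depression), physical health (physical function, fatigue, pain". Follow-up questionnaires arrive in a mailed packet, and the Study Flow table tells staff to "Ask survey preference (mail/online") when scheduling each follow-up.

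Section 11.0 lets staff refuse to start, or stop early, an individual performance test, and has the investigator consult on what to do after a serious event. Section 9.0 unlinks the Fitbit account when someone withdraws. Neither section mentions questionnaires after withdrawal. Section 10.0 plans an intent-to-treat primary analysis, multiple imputation without a stated model, and a linear mixed-effects model.

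**The concern.** Stopping an activity for safety and stopping measurement are different decisions, and section 12.0 joins them. A person who can no longer walk three blocks, or who starts treatment for a recurrence, may have good reason to stop the step goals and the chair stand test. Neither is a reason to stop answering eight questions on paper or online.

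The people removed by this rule are plausibly those whose function has fallen, so the missing score is related to its own value. An intent-to-treat analysis keeps such a person in the denominator but does not supply the score. Imputation and the mixed model can use earlier observations, but not a decline that follows the last of them unless other observed data predict it. The arm with more such withdrawals would look better than it is. The 20% attrition allowance protects precision and does nothing about this.

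At stake is the between-arm estimate of physical function, which section 10.0 intends to carry into the design of a larger trial. The week-13 contrast matters most, because by week 26 the waitlist arm has also received the intervention.

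**Working it through.** **Plan's own figure.** Section 10.0 states a two-sided two-sample t-test at 0.05, 25 per arm, a difference of 8.1, an SD of 10 and 80% power. The noncentral t distribution gives 80.1%, and 25/0.8 = 31.25 rounds up to 32 per arm. The plan's figures reproduce. The implied standard error of the difference is 10 × √(2/25) = 2.83 points.

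**Assumed inputs** (the documents give none of them):
- k, the number withdrawn for safety per arm: 1 to 3 of 32
- d, their decline after the last observed score: 3 to 10 points (10 is one SD)
- r, the share of the decline that imputation recovers

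**Formula.** With arms A and B and everyone analysed as randomised:

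bias = ((kA × dA − kB × dB)/32) × (1 − r)

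**Week 13.** Only withdrawals before week 13 count. The only earlier score is baseline, which precedes the decline, so r = 0.
- One arm only, minimum: (1/32) × 3 = 0.09 points
- One arm only, maximum: (3/32) × 10 = 0.94 points
- Relative to the standard error: 0.09/2.83 = 0.03 and 0.94/2.83 = 0.33
- Relative to the 8.1-point design difference: about 1% and 12%
- 2 versus 1, equal declines: (1/32) × 3 = 0.09 to (1/32) × 10 = 0.31 points
- Equal numbers and equal declines: 0

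**Week 26.** If the week-13 score was observed and already shows a fraction f of the decline, and all visits correlate equally at ρ, then r = f × ρ/(1 + ρ).

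| f | ρ = 0.5 | ρ = 0.7 |
|---|---|---|
| 0 | 0 | 0 |
| 0.5 | 0.17 | 0.21 |
| 1 | 0.33 | 0.41 |

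Recovery is therefore 0 to 41%. With one arm only, the range runs from (1/32) × 3 × 0.59 = 0.06 to 0.94 points.

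**Simulation check** (2,000,000 per scenario, 3 of 32 withdrawn, 10-point decline, ρ 0.5 to 0.7). Comparing completers only, the bias is 0.94 if withdrawal is unrelated to baseline. It is 1.37 to 1.54 if the log-odds of withdrawal rise by 1 per SD of lower baseline. Imputation from baseline brings it to 0.94; adding the week-13 score gives 0.55 to 0.94. Imputation thus removes the part explained by baseline but recovers at most 41% of the later decline. Baseline comorbidity might help further and was not modelled.

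**The case against.** The strongest case against is that this rests on silence. Section 12.0 does not forbid questionnaires after withdrawal, and the consent pages and the text between sections 17.0 and 19.0 were not available to read. A reader might infer that the scores are certain to be lost; the visible text supports only that they may be. What stands is that the written rule removes the person from the study and nothing visible brings the form back.

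Second, graded stopping already exists in part. Section 11.0 allows a single test to be withheld or stopped, so section 12.0 is the last step in a study classed as minimal risk, and few people may reach it. That is fair and limits the size. It does not help someone who does reach it.

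Third, the bias is small beside the noise: the planned 95% interval is roughly ±5.7 points (2.01 × 2.83). The 0.94 maximum needs three withdrawals in one arm, none in the other, and a full-SD decline in each. The fix would also not recover everything, since some of these people will not reply. All of this stands and sets the priority.

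Two stronger readings are tempting. One is that the intervention arm would lose more people because its coaches would notice decline. The documents do not show this: coaching calls are not described as safety screens, and the toll-free line and performance-test monitoring apply to both arms. The other is that anyone drifting outside an entry criterion, for example by becoming more active, must be withdrawn. The rule is conditional on safety, so decline is the plausible case.

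**Conclusion.** The point holds in limited form. As written, section 12.0 can remove a primary-outcome score from people who have plausibly declined, with no safety reason to stop the form.

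For the week-13 contrast the bias is 0.09 to 0.94 points if all withdrawals fall in one arm, 0.09 to 0.31 points for 2 versus 1, and about zero if numbers and declines are balanced. Week-26 losses may be partly recovered. These figures rest entirely on assumed withdrawal counts and declines, and on no predictor beyond earlier scores.

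A reader might infer that the trial's effect estimate is seriously compromised. The documents do not support that: the bias is probably small, imbalance between arms is not shown, and this is a feasibility study seeking preliminary estimates. It is a low-priority improvement, worth making because it costs little.

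**What to change.** Reword section 12.0 along these lines:

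> If the investigator judges that the step and active-hour goals, coaching or performance tests are no longer safe for a participant, those activities will stop. The participant stays in follow-up, and at least the 8-item PROMIS physical function form will be requested at weeks 13 and 26, by mail or online, unless the participant declines, withdraws consent or loses capacity to consent.

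The capacity exception matches section 3.3 ("Adults not able to consent are excluded from participation"). Make the other questionnaires and activPAL optional for these participants. Analyse everyone as randomised and report safety stops by arm; the adverse event log in section 11.0 already records the action and date for serious events. Relax the gift-card step in the Study Flow table for them, since it currently requires the activPAL return and the remote assessment as well as the surveys.

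The cost is a wording amendment with matching consent text. Each affected person adds at most two 8-item forms, some reminder contact, and up to 2 × $50 = $100 in cards that are already budgeted. The downsides are a small questionnaire burden on people who may be unwell, and the need to track intervention status separately from follow-up status.

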		X					Reminder to ppt about assessment (text from [name] with link to Zoom or Skype videoconference session for physical function tests)
							Remote assessment conducted / completed via Skype or Zoom

PROTOCOL TITLE: Whole-of-Day Approach to Physical Activity in Older Cancer Survivors

Fees/ Postage	Phone		Email		Mail		
	IN	OUT	IN	OUT	IN	OUT	
		X					Follow-up for incomplete surveys; return of activPAL (see Assessment Call 4 Script ...)
						X	Mail gift card (after verifying activPAL returned, and remote assessment AND surveys completed)
						X	Mail letter to immediate intervention group (maintain usual activity; next study contact in 12 weeks)
							Start intervention for waitlist control participants (Fitbit setup, 5 health coaching calls)
							26-week assessment 
 • Schedule remote assessment w/ [name] via MYHealth calendar • Ask survey preference (mail/online)
							Repeat steps from 13-week assessment
							Post-study telephone survey

NOTES:

¹ Whoever conducts the consent process signs the participants' form once received; for e-consent; print consent form, sign, photocopy and keep one copy in the ppt's folder; mail a copy of signed consent to ppt

² Whoever conducts the consent process signs the participants' form once received; for e-consent; print consent form, sign, photocopy and keep one copy in the ppt's folder, mail a copy to ppt

PROTOCOL TITLE: Whole-of-Day Approach to Physical Activity in Older Cancer Survivors

Outcomes and Measurements

All measures have well-established validity and reliability, and are responsive to change.

Table 2. Outcomes & Measures (B=baseline; P=1-week post-intervention; F=3-months post-intervention follow-up to assess maintenance of behavior change & effects)(alpha=Cronbach's alpha; ICC=intraclass correlation test-retest reliability; RMSEA=root mean square error of approximation; CFI: comparative fit index)	B	P	F
Process Data (primary outcomes): As this is a feasibility and acceptability study, the primary outcomes relate to recruitment, retention, adherence, and adverse events, which will be carefully tracked. Collected and used to evaluate adherence: steps per day/number of active hours (downloaded from Fitbit® website), satisfaction with the program, likes & dislikes, barriers & issues, perceived degree of benefit, and intervention fidelity (see above)		X	X

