10.0 Data and Specimen Management

Data Management

Each participant will be assigned a unique number to identify their data. This unique number will be placed on each document (questionnaires) and included in each electronic file name (accelerometer data files created by software used to download the data) to identify the participant.

Data from questionnaires will be entered into a REDCap database. Only essential study personnel will have access to this database. Data entry will be tied to the unique number assigned to the study participant.

Data from the activPAL accelerometers will be downloaded using the PAL Technologies software packages and stored on a secure data server at UNM. The files will be identified by unique study ID number and assessment (baseline, post-intervention, or 3-month follow-up).

A data collection form will be used by the study personnel conducting the remote assessment of physical performance. This form will be identified using the unique study ID number. Data from this form will be entered into the REDCap database.

All paper files, including consent forms, will be stored in locked drawers. All electronic files, including audio recordings and video recordings will be stored on a secure data sever at UNM. All electronic files will be destroyed 3 years after the study closes. .

Recorded audio files with the Health Coaches will be saved on a secure server at UNM and saved with the unique Study ID number.

Recorded videos of remote physical performance tests will be saved on a secure server at UNM and saved with the unique study ID number.

Statistical Analyses

Overview: Outcome variables violating the normality assumption will be transformed prior to analyses. The pattern of missing data will be evaluated,⁷³ and the appropriate procedures for multiple imputation will be utilized. Primary analyses will be performed according to the intent-to-treat principal; as this is a feasibility study, per-protocol analyses also will be explored. ActivPAL3™ data will be downloaded using associated software, and analyzed using SAS and R software. Raw and event data (start/stop time for sitting/lying, standing, and stepping) will be processed using standard methods, e.g., determining valid wear time,⁷⁴⁻⁷⁶ threshold values for activity intensity,^{27,77,78} etc. Standard compliance criteria will be used (≥ 4 days with ≥ 10 hours/day).^{27,79} Quality controls (daily logs, visual examination of heat maps) will be used to check

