11.0 Provisions to Monitor the Data to Ensure the Safety of Subjects

This study does not involve the testing of pharmacologic agents nor any therapeutic treatments. It is a behavioral intervention aimed at promoting physical activity using a whole-of-day approach, i.e., increasing light-intensity physical activity throughout the day while reducing and disrupting sedentary activities. Thus, it is classified as a Type 3 Study (Non-therapeutic, non-physical intervention), a minimal risk level study.

PROTOCOL TITLE: Whole-of-Day Approach to Physical Activity in Older Cancer Survivors

For the physical performance tests, the safety of subjects will be monitored in real-time, i.e., during the performance of the brief, timed tests. The study team will not allow the test to start or will stop it early if they believe there is a risk of injury to the participant, e.g., if participant is feeling dizzy, is not feeling well, or has recently suffered an injury that could affect the participant's ability to safely perform the tests.

Study participants will be encouraged to report any “emergencies or events” by calling the toll-free study number. Study staff will record all reported events in the adverse event log (including the subject’s name, date, and event description) and inform the principal investigator, [name], immediately of any unanticipated study deaths or serious events that potentially jeopardize participation in the study. [name] will consult with her mentors/Co-Investigators on the action that should be taken. This communication will occur within 24 hours (for an unanticipated study death), and four business days for an unanticipated serious event. This action and date of implementation also will be recorded in the adverse event log. During the quarterly meetings, the PI and her mentors will classify any reported events as “serious” or “non-serious” (see classification below), as well as “non-attributable”, “possibly attributable” or “attributable” to the intervention (unlike a pharmaceutical trial where known side effects exist, the classification of “expected” vs. “unexpected” is inappropriate for this behavioral intervention).

Serious—any event or condition that is life threatening, results in overnight hospitalization, cancer or a physical or cardiac event serious enough to require medical attention. A brief listing follows:

Fatal

Life threatening

Permanently disabling

Required or prolonged (overnight) hospitalization (Admission—not ER visit)

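### Section 12 ends all participation when the investigator judges it unsafe, with no stated provision to keep sending the physical-function questionnaire

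*Combined protocol and SAP*

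**What the plan says.** Section 12.0 has two sentences on withdrawal. Participants may leave when they wish. If the investigator thinks that taking part is no longer safe, the text continues: "i.e., the participant no longer meets the study eligibility criteria), the participant will be withdrawn from the study without their consent". The object of the withdrawal is the study, not the activity programme.

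Section 8.0 and Table 2 make self-reported physical function the primary effect outcome, beside the feasibility measures. Follow-up questionnaires go out by post at weeks 13 and 26, with a REDCap link as an option; the study flow in section 9.0 has staff do this when scheduling: "Ask survey preference (mail/online". For the analysis, section 10.0 states: "Primary analyses will be performed according to the intent-to-treat principal". It also plans multiple imputation after the missing-data pattern has been examined, and a linear mixed-effects model.

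The other available text on leaving the study covers replacement before randomization (section 4.0), unlinking the Fitbit account (section 9.0) and the right to drop out (section 24.0). None of it concerns questionnaires after an investigator withdrawal.

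A lesser safety step exists for the performance tests only. Section 11.0 says: "The study team will not allow the test to start or will stop it early if they believe there is a risk of injury".

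**The concern.** Stopping an activity programme and ending outcome collection are separate decisions, and section 12 joins them. A new injury may make extra steps or a chair-stand test unwise; it does not make a mailed form unwise.

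The loss is also likely to be informative. Section 12 explains unsafe by reference to eligibility, and the safety-related criteria in section 3.2 overlap the outcome. One is being "capable of walking 3 blocks (approximately 1300 steps or 0.25 mile) without an assistive device"; another is having no medical limitation to daily light activity. Section 13.0 links the two directly: "Individuals for whom unsupervised light-intensity activity is not appropriate will be excluded from the study per the eligibility criteria". People who cease to meet these criteria have probably lost physical function, which is what the questionnaire measures.

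At stake is the estimate for aim 1.1.b, which is meant to inform a larger trial. Scores that could have been collected would be missing, mostly from people who got worse. The retention figure in aim 1.1.a could also be affected, if exits imposed by the protocol count as non-retained.

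Loss could differ by arm as well. Before week 13 the intervention arm has a set-up call in week 2 and coaching calls in weeks 3, 5, 7, 9 and 11. The waitlist arm has no scheduled call until its week-13 assessment is arranged. In weeks 14 to 25 the pattern reverses.

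**Working it through.** **The plan's own figures.** Section 10.0 gives 25 per arm, SD 10, difference 8.1, two-sided 0.05 and 80% power. The two-sample t-test gives power 0.801 at 25 per arm and a detectable difference of 8.09. Allowing 20% attrition, 25/0.80 = 31.25, so 32 per arm and 64 in all. These reproduce; the sample size is not in question.

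**Standard error of the arm difference.** 10 × √(2/25) = 2.83.

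**Losses that 80% retention allows.** 52/64 = 81.3% meets the target and 51/64 = 79.7% does not, so 12 losses are allowed.

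**Assumptions, none of them in the plan.** A proportion q = 3% to 10% of each arm has a safety-relevant decline before week 13. A proportion d = 20% to 80% of decliners is withdrawn. Decliners score D = 5 to 15 T-score points below the rest.

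**Scores lost by week 13.**
- Whole trial: 64 × 0.03 × 0.20 = 0.4 to 64 × 0.10 × 0.80 = 5.1. Divided by 12, this is 3% to 43% of the retention allowance.
- Per arm: 32 × 0.03 × 0.20 = 0.2 to 32 × 0.10 × 0.80 = 2.6. The gap between 32 randomized and 25 in the power calculation is 7, so this is 3% to 37% of it.

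**Complete-case shift.** Among those still observed, the share of decliners is f(d) = q(1 − d)/(1 − qd). One arm's mean is too high by D × [q − f(d)]. The arm difference (intervention minus control) shifts by D × [f(d₀) − f(d₁)], where d₁ and d₀ are the proportions withdrawn in the intervention and control arms.

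| Withdrawn, intervention / control | q = 3%, D = 5 | q = 10%, D = 10 | q = 10%, D = 15 |
|---|---|---|---|
| equal | 0 | 0 | 0 |
| 80% / 50% | +0.05 | +0.31 | +0.46 |
| 80% / 20% | +0.09 | +0.60 | +0.90 |
| 20% / 50% | −0.04 | −0.29 | −0.44 |

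The largest entry in full: f(0.2) = 0.08/0.98 = 0.0816 and f(0.8) = 0.02/0.92 = 0.0217, so 15 × 0.0599 = 0.90. Reversing the arms gives −0.90.

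With equal withdrawal the difference does not move, but both arm means do. At D = 10 the excess runs from 10 × (0.03 − 0.0241) = 0.06 (q = 3%, d = 20%) to 10 × (0.10 − 0.0217) = 0.78 (q = 10%, d = 80%).

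**Scale.** 0.90/2.83 = 0.32 of a standard error in the most extreme case; the other unequal rows stay within 0.46/2.83 = 0.16.

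**The case against.** **Such withdrawals may not happen.** The study is classed as minimal risk, the activity is light, and people for whom it is unsuitable are screened out at entry. No withdrawal rate is given, and zero or one case among 64 is plausible. This stands: any cost is conditional.

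**Section 12 is discretionary and does not forbid further questionnaires.** Section 11.0 also leaves the response to serious events to consultation and lets single tests be stopped. True, but staff who follow a rule of withdrawal from the study would ordinarily stop mailing packets, and continued contact is best agreed beforehand. Consent pages, the text before section 1.0 and that between sections 17 and 19 were not available. If they already provide for follow-up, only section 12 needs aligning.

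**The planned analysis is not complete-case.** It uses multiple imputation and a repeated-measures model, adjusted for baseline as needed. This stands: the shifts above are not its bias. Imputation could use the logged event, but it may repair only part of a loss tied to declining health.

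**The gain is narrow.** Waitlist participants receive the full intervention after week 12, so week 26 has no untreated comparison. For the randomized contrast, the rescued scores matter mainly at week 13. This also stands.

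A reader might infer three stronger things that the documents do not support.
- That anyone drifting outside an entry criterion, including the PROMIS score range, must be removed. The sentence still requires a judgement that participation is unsafe, and no eligibility re-check is scheduled.
- That unequal staff contact biases the comparison. Either arm may phone in events, controls are called before the week-13 packet is mailed, and the direction is undetermined.
- That each such exit lowers the retention rate. Retention is not defined closely enough to say.

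**Conclusion.** The point holds as a conditional gap. As written, section 12 removes a participant from the whole study on a safety judgement, and no available text continues a risk-free primary-outcome questionnaire. If such withdrawals occur, the scores lost come from people likely to have declined.

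The size is modest and rests on assumed rates: 0.4 to 5.1 of 64 scores by week 13, or 3% to 43% of the 12 permitted losses if these exits count as non-retained. The true number may be zero. The illustrative complete-case shift in the arm difference is nil with equal withdrawal and at most about 0.9 points either way. The case for change is that avoidable, probably informative missing data can be prevented cheaply; it does not rest on a demonstrated bias or a shortfall in power. Low priority.

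**What to change.** Amend section 12.0 along these lines: if the investigator judges the activity programme unsafe for a participant in either arm, the activity goals stop (in the waitlist arm they are not started) and, where needed, so do the performance tests and monitor wear. The participant remains in the study and is still sent the week-13 and week-26 questionnaires, unless they ask to withdraw or can no longer consent. The safety judgement stays with the investigator.

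Two matching changes follow.
- The study flow in section 9.0 pays on this condition: "Mail gift card (after verifying activPAL returned, and remote assessment AND surveys completed". Waive the monitor and performance-test parts for these participants, so that completed questionnaires earn the card.
- Report safety stops by arm, separately from participants' own withdrawals. State whether participants stopped for safety count as retained; that definition is the sponsor's choice.

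Section 11.0 already says of the response to a serious event: "This action and date of implementation also will be recorded in the adverse event log". A further log field for how staff learned of the problem is optional.

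**Cost.** A short protocol amendment with matching English and Spanish consent wording, ethics approval, and possibly re-consent of those already enrolled. With up to about 5 such participants, the cards come to at most 5 × 2 × $50 = $500, already within the planned 64 × $150 = $9,600. No extra visits or calls are added, and the packets are already planned for everyone.
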